### 6.2.1 Inclusion criteria

Patients will be included in this study if they meet all of the following inclusion criteria:

1. Patient (adult or pediatric) is $\geq 2$ years of age *
2. Patient has a physician confirmed/documented diagnosis of PROS*
3. Patient has a documented evidence of a mutation in the PIK3CA gene*
4. Patient's condition was assessed by the treating physician as severe or life threatening and treatment was deemed necessary*
5. Patient has been treated with at least one dose of alpelisib, initiated on or before 23-Sep-2019 (i.e. at least 24 weeks before the cut-off date of the 09-Mar-2020)
6. Patient has medical chart history available during enrollment in the MAP
7. Patient (in case of pediatric patients assent and/or parent/guardian consent) consented to participate in the study (as required by local ethics regulations)
* Inclusion criteria for MAP enrollment (assessed at the time of alpelisib initiation).

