Concomitant medications (other than alpelisib) include medications starting on or after the index date or medications starting prior to the index date and continuing after index date. Concomitant medications will be coded using the World Health Organization (WHO) Drug Reference Listing (DRL) dictionary that employs the WHO Anatomical Therapeutic Chemical (ATC) classification system and summarized by lowest ATC class and preferred term using frequency counts and percentages.

Duration of alpelisib exposure, cumulative dose, dose intensity (DI) and relative dose intensity (RDI) will be summarized by age. The number of patients with dose reductions/interruptions, and the reasons, will be summarized and listed.

Duration of exposure to alpelisib defined as follow:

Duration of exposure (days) = (last date of know exposure to alpelisib) – (index date) + 1.

The last date of exposure is the last date when a nonzero dose of study drug is administered and recorded in the (e)CRF. For patients who are still receiving treatment at the time of cut-off date, the cut-off date will be used as last exposure date. The duration of exposure includes the periods of temporary interruption.

Summary of duration of exposure of alpelisib will include categorical and continuous summaries (i.e. mean, standard deviation etc.) using appropriate units of time (months).

Cumulative dose is defined as the total dose of the alpelisib given during the study. Cumulative dose will be summarized using descriptive statistics.

Dose intensity (DI) is defined as: $DI \text{ (mg/day)} = \text{Cumulative dose (mg)} / \text{Duration of exposure (days)}$.

Planned dose intensity (PDI) is the assigned dose by unit of time planned to be given to patients; at the start of treatment; generically 250 mg for adults and dose of 50 mg for pediatric patients are used per day.

Relative dose intensity (RDI) is defined as: $RDI \text{ (\%)} = DI \text{ (mg/day)} / PDI \text{ (mg/day)} * 100$

The number (%) of patients with dose reductions or interruptions and permanent discontinuations, and associated reasons, will be summarized.

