An important aspect of treatment with alpelisib consist in the healthcare resources needed to care for patients with PROS. The necessity for frequent hospitalization and ER visits could have both an economic and a general health impact on PROS patients. The analyses below aims to describe the pattern observed in the study population.

The proportion of patients using non-medical resource, hospitals and ER visits will be reported, along with the relation to the disease, during the study period.

Moreover the same measure will be assessed as available for the pre-index period and reported separately, to assess the use of HRU and ER visits prior to start of alpelisib.

Table 3-7 Endpoints related to objective #8.

Measure	Type of variable	Summary Statistics	Timing
Proportion of patients using non-medical resource (e.g., physical therapy, occupational therapy, home school)	Binary	Frequency, percentage	Overall during study period
Proportion of patients using non-medical resource due to PROS (i.e., related or not related)	Binary	Frequency, percentage	Overall during study period
Frequency of non-medical resource use	Categorical	Frequency, percentage	Overall during study period
Proportion of patients with ≥ 1 hospitalization	Binary	Frequency, percentage	Overall during study period
Proportion of patients with ≥ 1 hospitalization related to PROS (i.e., related or not related)	Binary	Frequency, percentage	Overall during study period
Number of hospitalizations	Continuous	N, mean, median, standard deviation, Q1, Q3, minimum and maximum	Overall during study period
Number of hospitalizations related to PROS	Continuous	N, mean, median, standard deviation, Q1, Q3, minimum and maximum	Overall during study period
Duration of hospitalizations	Continuous	N, mean, median, standard deviation, Q1, Q3, minimum and maximum	Overall during study period
Duration of hospitalizations related to PROS	Continuous	N, mean, median, standard deviation, Q1, Q3, minimum and maximum	Overall during study period
Proportion of patients with ≥ 1 ER visit	Binary	Frequency, percentage	Overall during study period
Proportion of patients with ≥ 1 ER visit related to PROS (i.e., related or not related)	Binary	Frequency, percentage	Overall during study period
Number of ER visits	Continuous	N, mean, median, standard deviation, Q1, Q3, minimum and maximum	Overall during study period

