4.3 Imputation rules

4.3.1 AE, ConMeds and safety assessment date imputation

Table 4-1 Imputation of start dates (AE, Symptoms and complications, concomitant medications medical history, health resources utilization, non-drug treatment and other medical interventions)

Missing Element	Rule
day, month, and year	
 • No imputation will be done for completely missing dates
day, month	
 • If available year = year of study treatment start date (index date) then 
 ○ If stop date contains a full date and stop date is earlier than study treatment start date then set start date = 01JanYYYY ○ Else set start date = study treatment start date. • If available year > year of study treatment start date then 01JanYYYY • If available year < year of study treatment start date then 01JulYYYY
Day	
 • If available month and year = month and year of study treatment start date then 
 ○ If stop date contains a full date and stop date is earlier than study treatment start date then set start date= 01MONYYYYY. ○ Else set start date = study treatment start date. • If available month and year > month and year of study treatment start date then 01MONYYYYY • If available month and year < month year of study treatment start date then 15MONYYYYY

Table 4-2 Imputation of end dates (AE, Symptoms and complications, concomitant medications, medical history, health resources utilization, non-drug treatment and other medical interventions)

Missing Element	Rule (*= earliest between (last treatment date plus 30 days, death date, cut-off date)
day, month, and year	
 Completely missing end dates (incl. ongoing events) will be imputed by the end date of the study period*
day, month	
 If partial end date contains year only, set end date = earliest of 31DecYYYY or end date of the study period*
Day	
 If partial end date contains month and year, set end date = earliest of last day of the month or end date of the study period*

Table 4-3 Imputation of start dates for assessments (Laboratory evaluation, vital signs, ECG, growth data, medical procedure (surgery), death, questionnaires, PROS disease history)

Missing Element	Rule
day, month, and year	
 No imputation will be done for completely missing dates

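### SAP Table 4-2 gives a hospital stay with no discharge date a length that runs to the end of the study period, even when the record is not marked ongoing

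*SAP*

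**What the plan says.** SAP 4.3.1 has one table for end dates, whose title reads "Imputation of end dates (AE, Symptoms and complications, concomitant medications, medical history, health resources utilization, non-drug treatment and other medical interventions". Three rows follow:

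- No date at all: "Completely missing end dates (incl. ongoing events) will be imputed by the end date of the study period". A note defines that end date as the "earliest between (last treatment date plus 30 days, death date, cut-off date".
- Year only: "If partial end date contains year only, set end date = earliest of 31DecYYYY or end date of the study period".
- Month and year: "If partial end date contains month and year, set end date = earliest of last day of the month or end date of the study period".

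No row treats hospital stays differently from adverse events. SAP 4.3.1.1 shows that an ongoing status is recorded separately from the end date, but it sets rules only for records whose start date is missing.

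Hospital duration is an objective 8 outcome. The objective 8 table in SAP 3.6 lists it for all stays and again as "Duration of hospitalizations related to PROS", as a continuous variable with mean, SD, quartiles, minimum and maximum. Protocol 6.8.2 asks for its mean and SD in the pre-index and study periods.

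SAP 3.6 and 3.6.2 both say that secondary endpoints are analysed without imputation. Section 3.6.2 adds that a missing parameter is simply not reported.

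**The concern.** Closing an open record at the end of observation makes sense for an event that is truly continuing, and it is a usual convention for adverse events. A hospital stay is different. If the chart shows an admission, no discharge date and no ongoing mark, the likely explanation is an incomplete record, not a patient who stayed in hospital until March 2020. The rule turns that gap into a length of stay.

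Protocol 6.9 expects incomplete recording because this is a chart review. Stays are probably few and mostly short, so one imputed length can dominate the mean, the SD and the maximum. The summary meant to describe the hospital burden on alpelisib would then largely reflect the time from an admission to the cut-off.

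The programmer also has two instructions that cannot both be followed for hospital duration: Table 4-2 fills the date, and 3.6.2 forbids filling it.

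**Working it through.** **Inputs.** The latest index date and the cut-off come from Protocol 6.2.1: "initiated on or before 23-Sep-2019 (i.e. at least 24 weeks before the cut-off date of the 09-Mar-2020". The imputed end date E comes from SAP Table 4-2. The SAP gives no formula for length of stay, so I assume the inclusive form it uses for duration of exposure: L = E − admission date + 1.

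**The plan's own figure.** From 23-Sep-2019 to 09-Mar-2020 is 7 + 31 + 30 + 31 + 31 + 29 + 9 = 168 days, and 168 / 7 = 24.0 weeks. This matches the protocol.

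**Imputed length, patient alive and on treatment at cut-off.** Here E is the cut-off date.

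| Follow-up from index | Admitted | L (days) |
|---|---|---|
| 24 weeks (minimum) | index | 168 − 0 + 1 = 169 |
| 24 weeks | week 4 | 168 − 28 + 1 = 141 |
| 24 weeks | week 12 | 168 − 84 + 1 = 85 |
| 24 weeks | week 20 | 168 − 140 + 1 = 29 |
| 24 weeks | week 23 | 168 − 161 + 1 = 8 |
| 52 weeks | index | 364 − 0 + 1 = 365 |
| 74 weeks (a window named in SAP 3.3) | index | 518 − 0 + 1 = 519 |
| 74 weeks | week 12 | 518 − 84 + 1 = 435 |

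**Patient who stopped early.** Here E is last treatment + 30 days. Treated for one day and admitted that day: 30 + 1 = 31 days. Treated for 8 weeks and admitted at week 6: 56 + 30 − 42 + 1 = 45 days.

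**Partial discharge dates.** These follow the other two rows. Admission on 15-Jan-2019 with only the year 2019 for discharge gives 31-Dec-2019, so L = 365 − 15 + 1 = 351 days. With month and year known, the error is at most about a month.

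**Effect on the mean (illustration).** The documents give neither the number of stays nor their length. Assume a true mean of 5 days and one discharge date missing.

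- 20 stays: mean = (19 × 5 + L) / 20. For L = 8, 85, 169, 519 this gives 5.15, 9.0, 13.2, 30.7 days.
- 10 stays: mean = (9 × 5 + L) / 10. For L = 85, 169, 519 this gives 13.0, 21.4, 56.4 days.

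With the affected stay left out of the duration summary, the mean remains 5 days in both cases. The maximum becomes L whenever L exceeds the longest real stay. The median and quartiles hardly move. Counts of stays and of patients hospitalized do not use the discharge date.

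**The same rule for a drug.** Take a drug started 20 weeks before a 23-Sep-2019 index with no stop date. If Table 4-2 is applied, the imputed stop is 09-Mar-2020. That falls after index, so the drug counts among "medications starting prior to the index date and continuing after index date" and is concomitant under SAP 3.6.

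**The case against.** **The no-imputation text may already protect hospital duration.** SAP 3.6.2 can be read that way, and the objective 8 table does not say that durations are built from imputed dates. But Table 4-2 names health resource use in its title, and nothing says which passage prevails. This is a contradiction to resolve, not a safeguard.

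**Data checks will find missing discharge dates.** Protocol 6.7 and 6.10 provide for queries, completeness checks and cross-checking of outliers with the sites. These should reduce the number. They cannot supply a date that the chart does not hold, and Table 4-2 governs whatever remains. The SAP's promise to show missing dates as missing covers adverse events and concomitant medications, and only in listings.

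**The size is hypothetical.** That stands. The number of affected stays is unknown, and an admission late in follow-up or in an early stopper is lengthened by only days or weeks.

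**Drugs and symptoms.** A reader might infer that the rule is equally wrong for these, and that records with an unknown end should stop at index. The documents do not support that remedy. In a single-arm before-and-after description, carrying an unknown end forward makes improvement harder to show. Ending such records at index would remove chronic symptoms and analgesics from later time-points and could create apparent improvement. That includes the pain-reduction indicator in SAP 3.6, which compares numbers of pain medications and pain conditions at index and Week 24. How far prior drugs collected since diagnosis pass through Table 4-2 is also not fully settled, because SAP 4.3.1 leaves pre-index details to the programming specifications.

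**Conclusion.** The concern holds for hospital duration. A stay with no discharge date and no ongoing mark is given an invented length, which enters the mean, SD and maximum of an objective 8 outcome. At minimum follow-up that length runs from 8 days (admission at week 23) to 169 days (admission at index) for a patient still on treatment at cut-off, and it can exceed 500 days with 74 weeks of follow-up. The lengths rest on the inclusive day count; the effect on the mean also rests on assumed numbers of stays.

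Three broader readings do not hold. Not every missing end date is sent to the end of the study period: only completely missing ones are, although a year-only date can still produce nearly a year. Not every affected stay becomes months or years long. And the drug and symptom carry-forward is not an error to be removed; what it lacks is a count of how many records depend on it.

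The effect is confined to descriptive secondary summaries. The primary response rate does not use these end dates. The change is still worth making, since it is cheap and the SAP contradicts itself as it stands.

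**What to change.** 1. In Table 4-2, restrict the end-of-study fill for hospital stays to records marked ongoing.
2. For any other stay with no discharge date, count the admission, leave the duration missing, and report how many durations are missing next to the summary.
3. Reconcile Table 4-2 with SAP 3.6 and 3.6.2, for example by stating that the no-imputation rule covers measured values and that date imputation follows section 4.3 with the hospital exception above.
4. For drugs and symptoms with a known pre-index start, no end date and no ongoing mark, keep the carry-forward as the main rule. Report how many records rest on an imputed end date, and add a sensitivity count without them.

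The cost is a change of wording in one table and two sections, a small programming change and a few extra counts. The downside is that a few hospital durations become missing.

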## **6 Research methods**

### **6.1 Study design**

This study will be a site-based retrospective non-interventional medical chart review of pediatric and adult male and female patients with PROS. This study will abstract longitudinal information that has been previously recorded in the medical charts of patients with PROS to assess the efficacy and safety of alpelisib for the treatment of the heterogeneous manifestations of PROS.

Patient-level data will be abstracted from medical charts of all eligible patients at all participating sites and will be pooled and assessed. Trained personnel at each site will abstract medical chart data (see [Section 6.4](#) for additional information). Informed consent will be obtained prior to data abstraction, as appropriate, for eligible patients interested in participating in the study.

[figure not shown]
Patients with PROS who have received at least one dose of alpelisib initiated at least 24 weeks before the cut-off date will be included. The index (baseline) date will be defined as the date of alpelisib initiation. The pre-index date period will be defined as the period from up to 24 weeks prior to the index date through one day prior to the index date. The study period will be defined as the period from the index date up to the cut-off date ([Figure 6-1](#)).

The cut-off date (09-Mar-2020) is selected to minimize the impact of the COVID-19 pandemic on the data integrity. Eligible patients who initiated alpelisib on or before 23-Sep-2019 will have relevant assessments expected to occur on or before 09-Mar-2020. At that time of the cut-off, COVID-19 pandemic did not have major consequences on the regular management of the patients in the countries participating in the MAP.

Available information from all clinic visits during the pre-index date period will be abstracted; additionally, available prior PROS medications and PROS related surgical/vascular interventions will be collected since diagnosis.

During the study period, all available data will be collected from index date up to the cut-off date. If a patient has discontinued treatment prior to that date, only data reported up to 30 days after the last date of study treatment will be abstracted and entered into the database.

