day, month	
 If available year = year of study treatment start date (index date) then set start date = max(study treatment start date, 01JulYYYY). If available year > year of study treatment start date then 01JanYYYY If available year < year of study treatment start date then max (01JulYYYY , Pre-Index date)
Day	
 o If available month and year = month and year of study treatment start date then set start date = max(study treatment start date, 15MONYYYY). • If available month and year > month and year of study treatment start date then 01MONYYYY • If available month and year < month year of study treatment start date then max(15MONYYYY , Pre-index date)

If imputed date is before birth or after DCO, death date or study discontinuation the last will be used.

If imputed end date is earlier than the start date or of the imputed start date then the imputed end date = start date.

Any AEs and ConMeds with partial/missing dates will be displayed as such in the data listings.

Any AEs and ConMeds which are continuing as per data cut-off will be shown as 'ongoing' rather than the end date provided.

For treatment start and end date if day is missing then it will be set to be the 15th of the month and if both month and day are missing, is defaulted to 01-Jan.

Treatment end date = min (imputed treatment end date*, death date, cut-off date).

If Imputed treatment end date < Treatment start date then Treatment end date= treatment start date.

Similar imputation will be performed for similar assessment in the pre-index period, more details as will be provided in the PDS.

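### SAP Table 4-3 floors partial dates of surgery and PROS disease history at the pre-index date, overriding the recorded year, and separately dates some index-year events on or after treatment start

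*SAP*

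**What the plan says.** Table 4-3 in SAP 4.3.1 is titled "Imputation of start dates for assessments (Laboratory evaluation, vital signs, ECG, growth data, medical procedure (surgery), death, questionnaires, PROS disease history". Surgery and PROS disease history therefore follow the same rules as laboratory tests and vital signs. Four of those rules matter here:

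- Month and day missing, year before the index year: "If available year < year of study treatment start date then max (01JulYYYY , Pre-Index date".
- Day missing, month before the index month: "If available month and year < month year of study treatment start date then max(15MONYYYY , Pre-index date".
- Month and day missing, index year: "If available year = year of study treatment start date (index date) then set start date = max(study treatment start date, 01JulYYYY".
- Day missing, index month: "then set start date = max(study treatment start date, 15MONYYYY".

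Pre-Index date is not defined as a single date. SAP 1.3 defines the pre-index period as running from 24 weeks before index to the day before index.

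Protocol 6.1 says that "available prior PROS medications and PROS related surgical/vascular interventions will be collected since diagnosis", and SAP 3.4 plans to report them over that same span. Protocol 6.3 lists the date of diagnosis among the clinical characteristics. Table 4-1, which covers medical history, non-drug treatment and other medical interventions, places a year-only date from an earlier year at 01-Jul of that year, with no floor.

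**The concern.** The pre-index floor makes sense for data abstracted only from the 24 weeks before index, because an earlier date cannot occur there. Surgery and disease history reach back to diagnosis, often by years. For them the floor does not settle an uncertain day or month. It discards the part of the date that is known.

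The floor at treatment start is a second, separate problem. In the index year or index month it cannot return a date before index, although the event may have preceded treatment. What is at stake is the dating of diagnosis and surgical history, and the on-study surgery measures under objective #5 (proportion of patients, type and number), all of which are reported over the study period.

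**Working it through.** **Inputs.** 24 weeks = 168 days, which agrees with the documents: 23-Sep-2019 + 168 days = 09-Mar-2020. The rules are those of Table 4-3. The index date 01-Jun-2019 is illustrative. Pre-Index date is read as index − 168 days; the day before index is checked as the alternative.

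**Earlier years and months.** 01-Jun-2019 − 168 days = 15-Dec-2018.

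| Recorded | Table 4-3 | Result |
|---|---|---|
| Diagnosis, 2008 | max(01-Jul-2008, 15-Dec-2018) | 15-Dec-2018 |
| Operation, 2012 | max(01-Jul-2012, 15-Dec-2018) | 15-Dec-2018 |
| Operation, May 2012 | max(15-May-2012, 15-Dec-2018) | 15-Dec-2018 |

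For the 2008 diagnosis, the imputed date lies 168/365.25 = 0.46 years before index. Mid-2008 would lie 3,987/365.25 = 10.9 years before index.

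The 01-Jul term can never win. The earliest floor for any index year comes from an index date of 01-Jan. August to December hold 31 + 30 + 31 + 30 + 31 = 153 days, and 168 − 153 = 15 days before 01-Aug is 17-Jul of the previous year, which is later than 01-Jul. So every year-only date from an earlier year becomes the Pre-Index date. When only the day is missing, the same happens whenever the 15th of the recorded month precedes the floor.

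If Pre-Index date means the day before index, the floor is 31-May-2019 and all three rows become that date. The conclusion is the same.

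**Index year and index month.**

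| Index | Recorded | Table 4-3 | Result |
|---|---|---|---|
| 01-Jun-2019 | 2019 | max(01-Jun-2019, 01-Jul-2019) | 01-Jul-2019, on study |
| 20-Jun-2019 | June 2019 | max(20-Jun-2019, 15-Jun-2019) | 20-Jun-2019, on study |
| 01-Jun-2019 | March 2019 | max(15-Mar-2019, 15-Dec-2018) | 15-Mar-2019, stays pre-index |

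The third row uses the pre-index floor, because March precedes the index month. The first two use the treatment-start floor.

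**All index dates.** The rules were applied to every index date from 01-Jan-2016 (an assumed start) to 23-Sep-2019.

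- Year-only dates in the 20 preceding calendar years: 100% equal the floor, under both readings.
- Day-missing dates at least two calendar years before the index year: 100% fall in the 24-week window.
- True pre-index events in the index year, month missing: 100% move on study, 99.9% of them to within 24 weeks after index.
- True pre-index events in the index month, day missing: 100% move on study.
- True pre-index events in an earlier month of the index year, day missing: 0% move on study.

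These percentages describe the rule. They do not estimate how many patients are affected.

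**Comparison within the SAP.** Protocol 6.3.2 gives sclerotherapy as an example of non-drug treatment, which Table 4-1 covers. A sclerotherapy recorded as 2012 becomes 01-Jul-2012. A debulking operation recorded as 2012 in the same patient becomes 15-Dec-2018 under Table 4-3. No reason is given for the difference.

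**The case against.** The strongest reply is that little planned output depends on these dates.

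- **Pre-index surgery.** SAP 3.4 reports prior surgery since diagnosis, and that count does not change when an old operation is re-dated within the time before index. The pre-index summaries it names are non-medical resource use, hospitalizations, ER visits and prior medication. Protocol 6.8.2 mentions surgery type next to the two periods for medication, but ambiguously. This stands: no output clearly sets surgery in the 24-week window against surgery on study.
- **Time since diagnosis.** Neither document specifies such a summary. This stands.
- **Convention and direction.** Table 4-1 also assigns ambiguous index-period dates to treatment unless a full stop date before treatment start shows otherwise, and over-counting on-study surgery works against the drug. That is fair as to direction. But a miscounted endpoint is still wrong, and the convention cannot apply to a diagnosis, which the inclusion criteria require at initiation.
- **Deferred detail.** The SAP leaves further pre-index detail to the programming specification, which is not available here. That document may add detail, but nothing in the protocol or SAP exempts the two variables, and Table 4-3 as written gives wrong dates.

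Complete dates are unaffected.

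**Conclusion.** The point holds for partial dates only. Table 4-3 sets every year-only date of surgery or disease history from an earlier year to the Pre-Index date, and likewise every day-missing date whose mid-month precedes the window. This contradicts the recorded year or month and does not fit a history collected and reported since diagnosis. The treatment-start floor can also add pre-treatment operations to the objective #5 surgery measures and date a diagnosis on or after treatment start.

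A reader might infer three stronger things that the documents do not support:

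- **That all earlier operations in the index year move on study.** Only those with the month missing, or with the day missing in the index month, do so.
- **That the before-and-after picture of surgery is flattered, or that reported disease duration collapses.** Any such summary built on these dates would be distorted, but neither is clearly planned.
- **That responders become non-responders.** Under SAP 3.5.1 rescue surgery must be due to deterioration while on alpelisib, so a re-dated operation does not qualify on its date alone. An effect is possible but not shown.

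The number of patients affected cannot be computed, because neither document gives the share of partial dates. The 15-Dec-2018 example assumes that Pre-Index date means index minus 24 weeks; the day before index leads to the same conclusion.

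**What to change.** Remove surgery and PROS disease history from the floored rule in Table 4-3 and give them their own row:

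- Month missing: 01-Jul of the recorded year. Day missing: the 15th of the recorded month. No pre-index floor. State this explicitly, because the default in SAP 4.3.1.2 would otherwise put a month-missing date at 01-Jan.
- Diagnosis with a partial date in the index year or index month: cap at the index date.
- Surgery with a partial date in the index year or index month: assign to the pre-index or study period from the eCRF page, or by site query where the page does not settle it.

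If the floor is kept for the other assessments, define Pre-Index date. The cost is an edit to one table, the matching programming change and a few site queries.
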